#### **9.1.1 Strength of Study Design**

The non-interventional design allows the observation of patients in a broad range of settings reflecting routine clinical practice. A prospective cohort design was chosen to reflect real-world characterization of patients with documented uterine fibroids and symptoms such as HMB treated long-term with Yselty®. The prospective nature of the study will allow for

the accurate measurement of exposure with the potential measurement of multiple outcomes as defined by the primary and exploratory endpoint measures.

### 9.1.2 Endpoints

The primary endpoint of objective **I**. is only assessed in patients with long-term treatment (>12 months) and is:

- Number and proportion of patients with a lumbar spine, total hip, or femoral neck BMD z-score below the threshold of -2 standard deviations.

The exploratory endpoints of this study are:

- For objective **II.a**:
  - Incidence rate of osteoporosis or fractures suspected to be due to osteoporosis; all suspected osteoporotic fractures (minimal- or non-traumatic) of long bones or spine where the physicians suspect an osteoporotic cause of the fracture
- For objective **II.b**:
  - Number and proportion of patients with elevated liver enzyme levels above the upper limit of normal
  - Incidence rate of adverse events suggestive of liver injury or related to liver enzyme elevation
- For objective **II.c**:
  - Incidence rate of adverse events regarding mood disorders including mood swings, affect lability, emotional disorder, irritability, mood altered, anxiety, bipolar disorder, mania, depression, depressed mood
- For objective **II.d**:
  - Incidence rate of uterine endometrial adenocarcinoma events
  - Incidence rate of mammary gland adenocarcinoma events

---

Additional analyses on ADRs will be performed.

 The RMP (see section 15.1) contains targeted follow-up questionnaires for these events. Physicians who report these events will be asked to fill the corresponding targeted follow-up questionnaire.

 The RMP (see section 15.1) contains targeted follow-up questionnaires for these events. Physicians who report these events will be asked to fill the corresponding targeted follow-up questionnaire.

 A list of MedDRA terms for hepatic events is available as a stand-alone document (see section 15.1).

- For objective **II.e**:
  - Number and proportion of patients starting each Yselyt® dosing regimen, time spent on each dosing regimen, and changes in dosing regimens
- For objective **II.f**:
  - Patient adherence to prescribed treatment, including ABT
- For objective **II.g**:
  - Incidence rate of adverse events for cardiac disorders (ventricular arrhythmias [e.g., ventricular tachycardia and ventricular fibrillation, flutter, torsade de points], cardiac arrest, and sudden cardiac death) suggestive of potential QT interval prolongation
  - Incidence rate of adverse events regarding electrocardiogram (ECG) findings indicative of QT interval prolongation, according to the physician's information
- For objective **II.h**:
  - Frequency of use of DXA scans in defined time periods:
    - Among patients with >1-year treatment, the number and proportion of Yselyt® users who received at least 1 DXA scan between 10 months until 14 months
    - Among patients with >2-year treatment, the number and proportion of Yselyt® users who received at least 2 DXA scans between 10 months until 26 months
    - Among patients with >3-year treatment, the number and proportion of Yselyt® users who received at least 3 DXA scans between 10 months until 38 months
    - Among patients with ≥4-year treatment, the number and proportion of Yselyt® users who received at least 4 DXA scans between 10 months until end of study
  - Frequency of DXA scans prior to treatment initiation in patients at high risk for osteoporosis or bone loss

---

 Additional analyses on ADRs will be performed.

 The RMP (see 15.1) contains targeted follow-up questionnaires for these events. Physicians who report these events will be asked to fill the corresponding targeted follow-up questionnaire.

 The RMP (see 15.1) contains targeted follow-up questionnaires for these events. Physicians who report these events will be asked to fill the corresponding targeted follow-up questionnaire.

 High risk patients will be identified by their treating physician as described in section 9.2.1.

- Number and proportion of patients who received Yselty® at a dose of 200 mg for more than 6 months without concomitant prescriptions for ABT at suitable time periods (e.g., 3-month intervals)
- For objective **II.i**:
  - Incidence rate of ADRs
  - Incidence rate of SADR
- For objective **II.j**:
  - Mean absolute and relative change in density (g/cm^2) and absolute value and relative change of BMD z-score and t-score from baseline (for patients with baseline DXA scan as per routine clinical practice – per SmPC only recommended for patients at high risk for osteoporosis or bone loss)
  - Mean absolute and relative change in density (g/cm^2) and absolute value and relative change of BMD z-score and t-score from DXA scan at 12 months (for patients with multiple follow-up DXA scans as per routine clinical practice)

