#### **Follow-up visit(s) for patients who experienced BMD decrease or osteoporosis during the study**

Patients who discontinued treatment with Yselty® but had BMD decrease or osteoporosis during the study should be observed in the study for up to 24 months after the last administration of Yselty®. Documentation of further visits by the physician during the further follow-up period will be limited to BMD assessments and relevant concomitant medications. For AE reporting please see section 11.3.

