### **9.3.6 Variables to Assess the Exploratory Endpoints**

The variables for the exploratory endpoints are:

- For objective **II.a**:
  - Osteoporosis diagnoses
  - Bone fracture events (long bones, spine)
  - For fractures, the probability of an osteoporotic cause of the fracture judged by the physician
  - Laboratory values of 25-hydroxy vitamin D, if available
- For objective **II.b**:
  - Laboratory values of liver enzyme levels or values indicative of liver injury such as alanine aminotransferase (ALT), aspartate aminotransferase (AST), bilirubin, gamma-glutamyl transferase (GGT), and alkaline phosphatase (ALP), if available
  - Date of laboratory assessment of liver enzyme levels, if performed
  - Elevated liver enzyme events
  - Events indicative of liver injury
- For objective **II.c**:
  - Mood disorder events of mood swings, affect lability, emotional disorder, irritability, mood altered, anxiety, bipolar disorder, mania, depression, depressed mood

- For objective **II.d**:
  - Uterine endometrial adenocarcinoma events
  - Mammary gland adenocarcinoma events
- For objective **II.e**:
  - Yselty® dosing regimen and changes in dosing regimens (see section 9.3.4)
- For objective **II.f**:
  - Reported patient adherence to prescribed treatment, including use of ABT
- For objective **II.g**:
  - Cardiac disorder events (ventricular arrhythmias [e.g., ventricular tachycardia and ventricular fibrillation, flutter, torsade de points], cardiac arrest, and sudden cardiac death) suggestive of potential QT interval prolongation
  - ECG findings indicative of QT interval prolongation, according to the physician's information
- For objective **II.h**:
  - DXA scan in defined time periods; Yes/No (see section 9.1.2)
  - DXA scan prior to treatment initiation in patients with risk factors for fractures, osteoporosis, or bone loss; Yes/No
  - Prescription of 200 mg Yselty® without concomitant ABT in defined time periods; Yes/No (see section 9.1.2)
- For objective **II.i**:
  - ADRs
  - SADR
- For objective **II.j**:
 

For patients with multiple DXA scans (at baseline and/or follow-up[s]):

  - BMD z-score and BMD t-score measured in lumbar spine, total hip, or femoral neck
  - Absolute value of density (g/cm^2)
  - Date of DXA scan, if performed
  - Anatomic site of DXA scan, machine type, imaging parameters of DXA scan, and reference population used, if available

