### **9.7.2 Study Population**

All analyses will be performed for the total study population (overall analysis). Separate analyses for each participating country will be provided if patient numbers are sufficient and if required for local reasons. In addition, data will be stratified whenever reasonable and dependent on the number of patients by the following parameters: country, age, race, dosing regimen, long- vs. short-term use of Yselyt®, and other relevant clinical characteristics and will be specified in the SAP.

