#### **9.7.3.4 Analysis of Exploratory Endpoints**

For incidence rates of osteoporosis or suspected osteoporosis-related bone fractures, the number and percentage of patients with fractures will be provided including 95% CIs.

The frequency of laboratory assessments of liver enzyme levels will be analysed by descriptive statistics. Laboratory values of liver enzyme levels will be assessed by means of descriptive statistics at each assessment time and by absolute and relative changes to

baseline. For rates of AEs indicative for liver injury and of liver enzyme elevation, the number and percentage of patients with these events and the total number of events as well as the EAIR (exposure adjusted incidence rate) will be provided including 95% CIs. A preliminary list of included liver enzyme elevation events is provided as a stand-alone document (see section 15.1), with complete specification to be done in the SAP based on the MedDRA coding system version available at the time of statistical analysis. The incidence rates, as well as the number and percentage of patients, are also presented for the subgroup of patients in whom the AEs were categorised as ADRs.

For rates of AEs indicative for mood disorders, the number and percentage of patients and the total number of events as well as the EAIR will be provided including 95% CIs. Events including the PTs mood swings, affect lability, emotional disorder, irritability, mood altered, anxiety, bipolar disorder, mania, depression, depressed mood will be specified in the SAP based on the MedDRA coding system version available at the time of statistical analysis. The incidence rates, as well as the number and percentage of patients, are also presented for the subgroup of patients in whom the AEs were categorised as ADRs.

For rates of uterine endometrial adenocarcinoma events and mammary gland adenocarcinoma events, the number and percentage of patients with each of these event categories and the total number of events in each category as well as the EAIR will be provided including 95% CIs for each category. Events contained in each category will be specified in the SAP based on the MedDRA coding system version available at the time of statistical analysis.

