Summary statistics for the treatment duration will be provided. The dosing regimen patterns and reasons for dosing regimen switch will be evaluated by descriptive statistics. Summary statistics will be provided for incidences and reasons for dosing regimen interruption or premature discontinuation of Yselyt® and/or ABT. A transition table will be provided to compare prescribed baseline regimens with prescribed end of study regimens.

For reported adherence to the prescribed treatment, documented deviations from the prescribed dosing regimen will be evaluated by descriptive statistics.

For rates of AEs regarding cardiac disorders (ventricular arrhythmias [e.g., ventricular tachycardia and ventricular fibrillation], cardiac arrest, and sudden cardiac death) indicative of potential QT prolongation, the number and percentage of patients with these events and total number of events as well as the EAIR will be provided including 95% CIs. Events indicative of potential QT interval prolongation will be specified in the SAP based on the MedDRA coding system version available at the time of statistical analysis. Number and percentage of patients with QT interval prolongation as reported by physicians following ECG measurement will be evaluated by descriptive statistics. The incidence rates, as well

---

Additional analyses on ADRs will be performed. Considered as special situations in this study. See definition at end of this section.

as the number and percentage of patients, are also presented for the subgroup of patients in whom the AEs were categorised as ADRs.

Frequency of DXA scans in defined time periods (see section 9.1.2) and frequency of DXA scans prior to treatment initiation in patients with risk factors for osteoporosis and bone loss will be evaluated by descriptive statistics. The results will also be displayed stratified by dose (100mg/100mg + ABT/200mg + ABT)

Number and percentage of patients with an initial treatment dose of 200 mg without ABT that are not treated with ABT after  $\geq 6$  months,  $\geq 9$  months,  $\geq 12$  months,  $\geq 15$  months (continuing at 3-month intervals) while continuing a 200 mg dose of Yselty® will be evaluated by descriptive statistics.

For ADRs and SADR, the incidence as well as EAIR, will be provided including 95% CIs on MedDRA system organ class (SOC) and preferred term (PT) level.

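### Objective II.a is defined as an incidence rate of osteoporosis or suspected osteoporotic fracture, but the analysis section fixes only the number and percentage of patients with fractures

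*Protocol*

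**What the plan says.** Section 9.1.2 states the II.a endpoint as "Incidence rate of osteoporosis or fractures suspected to be due to osteoporosis". It limits the fractures to those of long bones or spine where the physician suspects an osteoporotic cause. Section 9.3.6 lists "Osteoporosis diagnoses" as a II.a variable separate from the fracture events.

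The analysis sentence in section 9.7.3.4 reads: "For incidence rates of osteoporosis or suspected osteoporosis-related bone fractures, the number and percentage of patients with fractures will be provided including 95% CIs". For mood disorders the same section promises "the number and percentage of patients and the total number of events as well as the EAIR will be provided including 95% CIs". The hepatic, adenocarcinoma and cardiac-event endpoints get equivalent wording, and ADRs and SADRs get incidence and EAIR.

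Under objective II.g, section 9.1.2 also asks for an incidence rate of adverse events regarding "electrocardiogram (ECG) findings indicative of QT interval prolongation, according to the physician's information". The analysis given for it is "Number and percentage of patients with QT interval prolongation as reported by physicians following ECG measurement will be evaluated by descriptive statistics".

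Three other places matter:

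- Section 9.7.2 plans stratification, where reasonable and where numbers permit, by factors that include "country, age, race, dosing regimen, long- vs. short-term use of" the product.
- Section 9.2.6 ends observation at discontinuation for patients without BMD decrease or osteoporosis. Those who had either "should be observed in the study for up to 24 months after the last administration of" the product.
- Section 11.3 collects events to 30 days after the last dose in general, but keeps collecting bone-loss events, including fractures, in the extended group.

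**The concern.** The endpoint and its analysis do not match in two respects. A percentage of patients is not an incidence rate, and an output restricted to patients with fractures leaves out patients who meet the endpoint through an osteoporosis diagnosis alone. An SAP that follows 9.7.3.4 literally would not deliver what 9.1.2 defines.

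The difference matters because observation time varies widely between patients. Recruitment lasts up to 18 months per country, countries start as the product launches, and most patients leave when treatment stops. A group followed for longer shows a higher percentage at the same underlying rate, so percentages cannot be compared across country, regimen or duration strata. In addition, only patients already known to have bone loss are watched for fractures for up to 24 months off treatment. If those fractures enter the numerator, they come from one selected group.

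II.a is exploratory, but it is the clinical counterpart of the primary BMD question.

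**Working it through.** **Text comparison**

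| Endpoint (9.1.2) | Defined as | Output in 9.7.3.4 |
|---|---|---|
| II.a osteoporosis or suspected osteoporotic fracture | incidence rate | n and % of patients with fractures, 95% CI |
| II.b hepatic AEs | incidence rate | n, %, events, EAIR, 95% CI |
| II.c mood AEs | incidence rate | n, %, events, EAIR, 95% CI |
| II.d adenocarcinomas | incidence rate | n, %, events, EAIR, 95% CI |
| II.g cardiac AEs | incidence rate | n, %, events, EAIR, 95% CI |
| II.g ECG findings | incidence rate | n and % |
| II.i ADRs, SADRs | incidence rate | incidence, EAIR, 95% CI |

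The protocol therefore treats a percentage and an EAIR as different outputs. II.a and the ECG findings are the two that lack the EAIR.

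**Size of the distortion**

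The plan gives no figure to reproduce on this point, so what follows is an illustration.

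Inputs from the protocol:
- Start of data collection Q1/Q2 2026 and end Q3/Q4 2029 (section 6).
- Recruitment of up to 18 months (section 6).
- Dropout of 20% per year (section 9.5).
- Events collected to 30 days after the last dose (section 11.3).

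Assumptions: milestone midpoints (April 2026 to October 2029, 3.5 years), one 18-month entry period with even entry, a constant dropout hazard, and a constant event rate low enough for the percentage to be proportional to person-time. Follow-up T then runs from 3.5 − 1.5 = 2.0 to 3.5 years.

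With yearly dropout d, the hazard is l = −ln(1 − d), and mean person-years over T years are (1 − (1 − d)^T)/l. For d = 0.2, l = 0.2231.

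- Earliest entry, T = 3.5: (1 − 0.8^3.5)/0.2231 = 2.43.
- Latest entry, T = 2.0: (1 − 0.64)/0.2231 = 1.61.
- Ratio: 2.43/1.61 = 1.51.
- Average over T uniform on 2.0 to 3.5: 2.04 person-years per patient.

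For long- versus short-term use, assume further that dropout means stopping treatment and that short-term means 12 months or less.

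- Short-term (20% of patients): mean time to stopping, given stopping within one year, is 1/l − 0.8/0.2 = 0.481 years. Adding 30 days gives 0.564.
- Long-term: 1 + the average of (1 − 0.8^(T−1))/l over T from 2.0 to 3.5 = 2.435. Adding 30 days for those who stop before study end gives 2.461.
- Ratio: 2.461/0.564 = 4.37.
- Check, without the 30 days: 0.2 × 0.481 + 0.8 × 2.435 = 2.04, the overall mean above.
- Other dropout rates: 2.604/0.573 = 4.54 at 10% and 2.321/0.552 = 4.20 at 30%.

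**The two measures side by side**

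Suppose five patients have one event each among 1,000 enrolled. The percentage is 0.50% (95% CI 0.16 to 1.16%). The rate is 5/2,044 person-years = 0.24 per 100 person-years (0.08 to 0.57).

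Suppose instead a fixed rate of 5 per 1,000 person-years, which is an assumed value. The expected percentage runs from 0.62% (40% yearly dropout, 2 years) to 1.45% (10% yearly dropout, 3.5 years), while the EAIR stays at 5.0 per 1,000 person-years.

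**The case against.** The strongest reply is that this is a one-line drafting slip with little practical loss.

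- **EAIRs exist elsewhere.** Section 9.7.3.5 provides EAIRs with 95% CIs for all AEs by SOC and preferred term, so osteoporosis and individual fracture terms should each receive a rate. This stands as partial mitigation. Those tables do not pool the composite, and they do not apply the restriction to long-bone or spine fractures that the physician suspects are osteoporotic.
- **The objective says incidence.** Section 8 words II.a as incidence, which a crude percentage can express. The endpoint in 9.1.2 nevertheless says incidence rate, and the analysis sentence itself opens with incidence rates.
- **The SAP may settle it.** That would hold if the protocol had left the output open. Here it fixes one that conflicts with its own endpoint.
- **The ECG findings may be covered.** A later sentence in the same paragraph mentions incidence rates, but it concerns the subgroup of AEs categorised as ADRs. The overall ECG endpoint is left with number and percentage.
- **The fold differences are stylised.** This stands in part. Earliest versus latest entry is not itself a planned stratum, and it carries over to countries only as far as their starts differ. In the long- versus short-term contrast unequal exposure is built in. An EAIR does not fully repair it, because long-term users must stay on treatment for 12 months to qualify and the hazard may rise over time.
- **Extension fractures may not be counted.** The protocol does not say whether they enter the II.a numerator. In a composite count, a patient kept for osteoporosis is already a case. But the output as written counts fractures, so a late fracture in a patient kept for osteoporosis or BMD decrease would add to it.

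**Conclusion.** The concern holds. Sections 9.1.2 and 9.7.3.4 contradict each other on II.a: the stated analysis yields neither a rate nor a result for osteoporosis-only cases. The II.g ECG endpoint also lacks its rate.

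The distortion is about 1.5-fold between earliest and latest entrants and about 4.4-fold (4.2 to 4.5 for 30% to 10% yearly dropout) between long- and short-term users. These figures rest on the assumptions listed above and illustrate the size. The textual contradiction does not depend on them. The consequence is minor to moderate, since the endpoint is exploratory, no sizing uses it, and the tables in 9.7.3.5 recover part of the information. It should be corrected before the SAP is finalised.

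**What to change.** In section 9.7.3.4, replace the II.a sentence with a commitment to the number and percentage of patients, the total number of events and the EAIR, each with 95% CI where applicable. Report these for the II.a composite as defined in 9.1.2, and separately for osteoporosis diagnoses and for suspected osteoporotic fractures. Count events and time at risk up to 30 days after the last dose, in line with section 11.3, and present later events from the extended follow-up separately. For the II.g ECG findings, add the total number of events and the EAIR with 95% CI.

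The cost is two sentences and a few table rows. Treatment start and stop dates, diagnoses and fracture events are already collected. Few events will give wide intervals, and an EAIR assumes a constant rate over treatment time, so the number and percentage should stay beside it. Comparisons of long- with short-term users will still need cautious reading.

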### **9.2.3 Exclusion Criteria**

- Patients who have ever used another GnRH antagonist (e.g., relugolix, elagolix) before enrolment
- Contraindications as per the approved SmPC
- Enrolment in a prior clinical trial with Yselty®
- Patients participating in an investigational program with interventions outside of routine clinical practice

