**Table 1 Estimated schedule for the Yselty® PASS**

	First Visit (Enrolment)	Baseline (Yselty® Treatment Start) 	Observation Time Points  (Months Since Yselty® Treatment Start)			
			12	24	36	48
Assessment of inclusion/exclusion criteria	X	–	–	–	–	–
Date of signed informed consent	X	–	–	–	–	–
Date of first Yselty® dose	–	X	–	–	–	–
Year of birth	X	–	–	–	–	–
Sex	X	–	–	–	–	–
Height/weight	X	–	–	–	–	–
Yselty® dosing regimen (100 mg without ABT, 100 mg with ABT, or 200 mg with ABT)	X	–	X	X	X	X
Medical history	X	–	–	–	–	–
Concomitant diseases	X	X				
Alcohol/nicotine/drug/stimulant consumption	X	–	X	X	X	X
Relevant prior medication	X	–	–	–	–	–
Relevant concomitant medication	X	–	X	X	X	X
BMD assessment, including absolute density values, z-score/t-score values, DXA scan date, anatomic site of DXA scan, machine type, imaging parameters, reference population used (if available)	X	–	X	X	X	X
Clinical evaluation (including weight, blood pressure, clinical assessment of fibroid)	X	–	X	X	X	X
Change in Yselty® dosing regimen, reasons for change	–	–	X	X	X	X
Reported adherence to prescribed treatment	–	–	X	X	X	X
Laboratory values  and date of laboratory assessment (if available)	X	–	X	X	X	X
Liver enzyme elevation events 	X	–	X	X	X	X
Bone fracture events 	X	–	X	X	X	X
Events of uterine endometrial adenocarcinoma and mammary gland adenocarcinoma	X	–	X	X	X	X

	First Visit (Enrolment)	Baseline (Yselty® Treatment Start) 	Observation Time Points  (Months Since Yselty® Treatment Start)			
			12	24	36	48
Mood disorder events 	X	–	X	X	X	X
Cardiac disorder events suggestive of potential QT interval prolongation	X	–	X	X	X	X
ECG findings indicative of QT interval prolongation, according to the physician's information	X	–	X	X	X	X
RMP targeted follow-up questionnaires on uterine endometrial and mammary gland adenocarcinoma, QT interval prolongation, exposure in pregnancy/pregnancy outcome, cases of elevated liver enzymes 			X	X	X	X
AEs, SAEs, ADRs, SADRs, special situations 	X	–	X	X	X	X
Premature discontinuation, including reasons 	–	–	X	X	X	X

1 Date of first visit (enrolment) and date of first Yselty® dose (baseline) may be the same, or the date of first Yselty® dose may be up to 3 months prior to first visit. For patients with first Yselty® treatment before enrolment, baseline data can be documented retrospectively at enrolment.

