2 This is the expected visit schedule, however, visits are to be performed as per routine practice. Additional visits can also be recorded. In case the observational period per country is prolonged, data collection will be prolonged as well.

3 Laboratory values include 25-hydroxy vitamin D, if available, and liver enzyme levels or values indicative of liver injury such as ALT, AST, bilirubin, GGT, and ALP, if available.

4 A list of MedDRA terms for hepatic events is available as a stand-alone document (see section 15.1) and will be further specified in the SAP.

5 Including events of osteoporosis or fractures suspected to be due to osteoporosis; all suspected osteoporotic fractures (minimal- or non-traumatic) of long bones or spine where the physicians suspect an osteoporotic cause of the fracture.

6 Including events of mood swings, affect lability, emotional disorder, irritability, mood altered, anxiety, bipolar disorder, mania, depression, depressed mood.

7 The RMP (see section 15.1) contains a targeted follow-up questionnaire for events indicative of uterine endometrial and mammary gland adenocarcinoma, QT interval prolongation, exposure in pregnancy/pregnancy outcome, and cases of elevated liver enzymes. Physicians who report an event indicative of these events will be sent the appropriate targeted follow-up questionnaire.

8 In case of discontinuation, AEs, SAEs, ADRs, SADRs, and special situations have to be documented as outlined in section 11.3.

9 Special situations include drug interactions, medication abuse, medication misuse, medication overdose, medication errors, unexpected therapeutic or clinical benefit from product use, pregnancy or lactation exposure with the product, lack of efficacy, off-label use, and occupational exposure (see section 11.4).

10 Physicians should continue to document BMD measurements during the extended follow-up period for patients who experienced BMD decrease or osteoporosis during the study. Management of AE/ADR occurring after treatment discontinuation will be managed in accordance with section 11.3.

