### **9.3.2 Comorbidities (Medical History, Concomitant Diseases)**

Comorbidities are any relevant medical findings that were present before start of therapy with Yselty®, independent of whether or not they are still present. They have to be documented in the Medical History/Concomitant Diseases section of the eCRF at the enrolment visit. Specific medical history will be collected on initial diagnosis, history of disease, history of an indication for surgical treatment of fibroids, as well as in the categories of:

- Previous fracture
- Mood disorders, including family history
- Hepatic disorders
- Cardiac disorders
- Malignant carcinoma
- Other relevant risk factors for osteoporosis or bone loss (including alcohol abuse, smoking, obesity, strong family history of osteoporosis, type I diabetes mellitus, rheumatoid arthritis, Vitamin D absorption disorders, Paget disease, osteogenesis imperfecta in adults, chronic kidney disease, untreated long-standing hyperthyroidism, chronic malnutrition, or malabsorption and chronic liver disease and long-term use of systemic steroids)

For any comorbidity, the diagnosis and if the disease is still ongoing at time of enrolment visit have to be documented.

---

 Date of first visit (enrolment) and date of first Yselty® dose (baseline) may be the same, or the date of first Yselty® dose may be up to 3 months prior to the first visit.

A clinical evaluation, including body weight, blood pressure, and clinical assessment of the fibroid, will be performed at enrolment visit and at follow-up visits, as per routine clinical practice.

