#### **9.7.3.3 Analysis of Primary Endpoint**

The primary objective will only be assessed in users with the long-term treatment (>12 months) and where z-scores of lumbar spine, total hip, or femoral neck are available. For rates of events of BMD z-scores below the age-related threshold of -2 standard deviations, the number and percentage of patients with these events will be provided including 95% CIs.

The aggregated number, frequency of DXA scans, anatomic site of DXA scan, machine type, and imaging parameters of DXA scans during the observational period will be analysed by descriptive statistics. If results of DXA scans can be interpreted in a categorised way, shift tables for the change from baseline, will be provided, where available. If images of the DXA scans can be provided by the doctors, they will be reviewed by 1 independent expert for their suitability and included in an additional sensitivity analysis.

Sensitivity analyses using different criteria (e.g., machine type) to select DXA scans that ensure their comparability will be performed to evaluate the primary endpoint if the sample size allows (e.g., if more than 30 patients remain after selection of suitable cases) and will be further detailed in the SAP.

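### Cheap improvement: the II.b liver laboratory endpoint has one cut-off, above 1 x ULN, so it counts trivial and severe rises alike

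*Protocol*

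**What the plan says.** Section 9.1.2 gives objective II.b two endpoints. The laboratory one is "Number and proportion of patients with elevated liver enzyme levels above the upper limit of normal"; section 8 uses the same limit in the objective. The other is an incidence rate of liver-related adverse events.

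The measurements come from routine care. Table 1, footnote 3, lists "liver enzyme levels or values indicative of liver injury such as ALT, AST, bilirubin, GGT, and ALP, if available". Section 9.3.6 adds the date of the liver enzyme assessment.

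For the analysis, section 9.7.3.4 plans the frequency of testing, descriptive statistics at each assessment, and absolute and relative changes from baseline. Section 9.7.2 makes the total study population the default, and 9.7.1 shows missing data as a separate category without imputation.

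The endpoints based on bone scans are worded differently. The primary endpoint is assessed "where z-scores of lumbar spine, total hip, or femoral neck are available" (9.7.3.3), and the first part of II.j is "for patients with baseline DXA scan as per routine clinical practice". II.b has no such restriction.

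**The concern.** Slightly raised enzymes are common and often mean little. A liver safety assessment needs to know how many women had a large rise, and how many had a transaminase and bilirubin raised together. This is the study's only liver endpoint based on measured values, and it answers neither question. The sponsor already treats elevated liver enzymes as important enough for a targeted questionnaire, and the values needed for a graded count are being collected.

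Two lesser matters follow from the wording. The proportion may depend on how many women were tested, which 9.7.1 itself expects to vary with local standards of care. The count also does not separate women whose enzymes were raised before the first dose.

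**Working it through.** The plan gives no figure for II.b to reproduce; Table 2 concerns the bone density endpoint only. The main check is therefore of the text, followed by three illustrative calculations.

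**1. Does any stated output count women by size of rise?**

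- Laboratory endpoint (9.1.2): one category, above ULN. No.
- Frequency of testing (9.7.3.4): counts tests, not results. No.
- Descriptive statistics and changes from baseline (9.7.3.4, with the statistics listed in 9.7.1): one maximum per analyte and time point. This shows that a large value occurred, not how many women had one, and says nothing about two analytes in the same woman.
- Liver adverse event rate (9.7.3.4): counts patients and events, but combines injury with enzyme elevation and depends on physicians reporting them.
- Preferred-term tables of AEs, SAEs, ADRs and SADRs (9.7.3.5): separate coded injury from coded enzyme elevation, but again only for reported events and without grading by ULN.
- RMP questionnaire (9.4): sent only after a physician reports an event.

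None does.

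**2. How many women could exceed 1 x ULN with no drug effect?** Assume, since the documents do not say, that ULN is the 97.5th percentile in healthy women. With independent results, the chance of at least one exceedance is 1 - 0.975^(analytes x tests).

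- 1 analyte, 1 test: 2.5%
- 5 analytes (those in footnote 3), 1 test: 1 - 0.975^5 = 11.9%
- 5 analytes, 4 tests (12, 24, 36 and 48 months): 1 - 0.975^20 = 39.7%

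Independence overstates the last two. With complete dependence the figure stays at 2.5%, so the plausible range is wide: 2.5% to 39.7%.

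**3. Denominator.** Proportion of all women = tested share x proportion in tested. Assume 10% of tested women exceed ULN and 1,000 are enrolled. Exact (Clopper-Pearson) 95% intervals are shown.

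| Tested | Over all enrolled | Over tested |
|---|---|---|
| 300 | 30/1,000 = 3.0% (2.03 to 4.26) | 30/300 = 10.0% (6.85 to 13.97) |
| 800 | 80/1,000 = 8.0% (6.39 to 9.86) | 80/800 = 10.0% (8.01 to 12.29) |

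The number of women affected does not change; the proportion and its interval do.

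**4. If no woman meets the joint criterion.** The upper limit of the two-sided 95% interval is 1 - 0.025^(1/n): 0.37% for n = 1,000, 0.46% for n = 800 and 1.22% for n = 300. The reassurance depends on the number tested, so that number must stand beside the result.

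**5. Timing.** Laboratory values are also recorded at enrolment, and the first dose "may be up to 3 months prior to first visit" (Table 1, footnote 1). An enrolment value can therefore fall before or after the first dose, and only its date tells which.

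**The case against.** The strongest reply is that ULN multiples, denominators and baseline flags are table content, which 9.7.1 leaves to the analysis plan. Nothing in 9.1.2 forbids finer categories, and that plan is not shown. This stands in part: no one can say that the final tables will lack a graded count. But the cut-off itself is an endpoint definition fixed in the protocol, and nothing there commits to more.

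It is also fair that the thresholds proposed here are convention rather than taken from the documents, and that high categories may be sparse when testing is ad hoc.

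A reader might infer more than the documents support:

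- That severe liver reactions would go unseen. Preferred-term tables, serious event tables, the ADR subset and the questionnaire would show those that physicians report.
- That the proportion is irretrievably diluted. The missing category and the test frequency let a reader recover the tested share. Section 9.7.2 also contrasts the total population with countries and strata, so using it as the II.b denominator is an inference.
- That earlier elevations cannot be identified. Changes from baseline are planned, and the dates of liver tests and of the first dose are collected. Section 9.3.2 records hepatic disorders, and its risk-factor list ends with "or malabsorption and chronic liver disease and long-term use of systemic steroids". What is missing is a split of the II.b count.
- That women with liver disease enter freely. Section 9.2.3 excludes "Contraindications as per the approved SmPC", whose content is not shown.
- That values after treatment distort the count. Further follow-up documentation is "limited to BMD assessments and relevant concomitant medications", and for other women observation ends with treatment, so this is not material.

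**Conclusion.** The point holds as a low-severity, optional improvement. The II.b laboratory endpoint treats trivial and severe rises alike, and no laboratory output stated in the protocol counts women by size of rise or with ALT/AST and bilirubin raised together. That rests on the text alone. How many trivial rises would be counted cannot be derived from the documents.

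The denominator is secondary. The contrast of 3.0% or 8.0% with 10.0% rests on an assumed 10% rate, assumed testing of 300 or 800 women, and the total population as denominator. The consequence is limited because the endpoint is exploratory and descriptive.

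**What to change.** In 9.1.2 and 9.7.3.4:

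- Keep above ULN as the lowest category, reported per analyte.
- For ALT and AST, add the number of women whose maximum value after the first dose is >=3, >=5 and >=10 x ULN.
- Add the number with ALT or AST >=3 x ULN together with bilirubin >=2 x ULN.
- Use as denominator the women with at least one test of that analyte after the first dose (of both components for the joint count), and show the number tested.
- Show women already raised before the first dose separately, classified by test date rather than by visit.

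The cost is a few extra tables from values and dates already collected, using the ULN that the present endpoint needs anyway. No additional visits or tests are required. The downside is small counts in the high categories.
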